3.7.1.2 Analysis

The following dose regimes will be summarised for ORR: “100 / 20” and “40 / 15”.

For ORR (achieved independent of time), the following will be presented:

- The responses of CR, PR, SD, PD, NE and ND for each dosing regimen.
- The number and percentage of responders for each dosing regimen together with the exact 95% CI using the Clopper-Pearson method.

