5.3 Part B – FL Phase IIb “PARADIGME”

5.3.1 Primary Objectives

The primary objectives are:

- Randomised section:
 - To evaluate the efficacy of the “40/15” dose regimen (40 mg lilotomab/ 15 MBq/kg Betalutin) compared with the “100/20” dose regimen (100 mg/m² lilotomab/20 MBq/kg Betalutin) based on the Independent Review Committee (IRC) assessment of tumour response rates in adult patients with relapsed rituximab/anti-CD20-refractory FL.
- Selected regimen for further development:
 - To evaluate the ORR of the 40/15 regimen based on the IRC assessment of tumour response rates in adult patients with relapsed rituximab/anti-CD20 refractory FL.

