14.1.7 Analysis of Efficacy Data

Tumour response will be reported as follows in individual patients:

- CR
- PR
- SD
- PD
- NE

In Part A and Part C: Response rate will be presented as a point estimate of the proportion of responders along with the 95 % exact confidence interval of response rate.

In Part B randomised period: The ORR will be compared between dosing regimens using the Fisher's Exact test, and the difference in response rates and the corresponding 95% exact CI will be presented. ORR estimates and 95% exact CI for each dosing regimen will also be presented.

In Part B Single-arm 40/15 part: – The primary efficacy analysis on ORR (based on independent assessment) will be performed by testing whether the ORR is less than or equal to 30% against the alternative hypothesis that ORR is greater than 20% at overall two-sided 5% level of significance, i.e.,

$H_0: p = 0.3$ vs. $H_a: p \neq 0.3$

In addition, the secondary efficacy analysis on CRR (based on independent assessment) will be performed by testing whether the CRR is less than or equal to 8% against the alternative hypothesis that ORR is greater than 8% at overall two-sided 5% level of significance, i.e.,

H0: $p = 0.08$ vs. Ha: $p \neq 0.08$

Responders are defined as having CR and PR according to definition in [Section 12.3](#).

Time to event endpoints will be analysed using standard Kaplan-Meier techniques. The estimate of the median survival curve will be calculated along with the associated 95% confidence intervals (when applicable). The efficacy endpoints are:

Overall Response Rate (ORR)

ORR, defined as the proportion of patients who achieve a CR or PR assessed with the use of standard criteria for lymphoma (1). The ORR will be assessed at 3 months image evaluation.

Best ORR will also be evaluated, taking the best response achieved independent of time point for image evaluation.

Complete Response Rate (CRR)

CRR, defined as the proportion of patients who achieve a CR assessed with the use of standard criteria for lymphoma (1). The CRR will be calculated based on complete responses achieved at any timepoint.

Progression-free survival (PFS)

PFS is defined as the interval from Betalutin administration and date of:

- Relapse (new or enlarged lesions after CR).
- Progression (new or enlarged lesions after PR or SD).
- Death from any cause.

If none of the above events are observed, PFS will be censored at the date of the last adequate tumour assessment

Duration of response (DoR)

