CRR	Complete Response Rate
CSR	Clinical Study Report
CT	Computed Tomography
CTCAE	Common Terminology Criteria for Adverse Events
DoCR	Duration of Complete Response
DoR	Duration of Response
ECG	Electrocardiography
ECOG	Eastern Cooperative Oncology Group
eCRF	Electronic Case Report Form
EU	European Union
FACT-Lym	Functional Assessment of Cancer Therapy–Lymphoma
FL	Follicular Lymphoma
γ GT	Gamma Glutamyl Transferase

HAMA	Human Anti-Murine Antibody / Human Anti-Mouse Antibody
HLA	Human leucocyte antigen
IRC	Independent Review Committee
ITT	Intent-To-Treat
LDH	Lactate Dehydrogenase
MBq	Mega Becquerel
MedDRA	Medical Dictionary for Regulatory Authorities
N/A	Not Applicable
NAb	Neutralising Antibody
NE	Not Evaluable
iNHL	indolent Non-Hodgkin Lymphoma
ORR	Overall Response Rate
OS	Overall Survival
PD	Progressive Disease
PFS	Progression-free Survival
PET	Positron-emission Tomography
PK	Pharmacokinetic
PR	Partial Remission
PT	Preferred Term
QoL	Quality of Life
RoW	Rest of World
SAE	Serious Adverse Event
SAF	Safety Analysis Set
SAP	Statistical Analysis Plan
SCT	Stem Cell Transplant
SD	Stable Disease
SI	International System of Units

SOC	System Organ Class
SPECT	Single Photon Emission Computed Tomography
SRC	Safety Review Committee
TEAE	Treatment Emergent Adverse Event
TFLs	Tables, Figures and Listings
WHO	World Health Organization

1 Introduction

This abbreviated statistical analysis plan (SAP) details the proposed analyses to be conducted by Veristat for the LYMRIT-37-01 phase I/II study (Part B) and the phase IIa expansion part (Part C).

Part A, dedicated to assessing the safety of various doses/regimens, was analysed under a separate SAP, Veristat study no: NOR18001.

In July 2022, LYMRIT-37-01 Part B and Part C were both terminated following slow recruitment. An ad hoc efficacy review of 61 patients (July 2022) who had received a dose of “40/15” and also had an Independent Review Committee (IRC) evaluated baseline and 3 month scan and efficacy assessment was conducted. Following this, the decision was taken to terminate the study. Details of this interim analysis are documented separately.

This analysis will be restricted to:

To support the final (close out) CSR, the efficacy and safety will be evaluated at a minimum of 3 months follow-up after the final patient has received the “40/15” regimen in Part B.

Specifically, this means that the following data will be formally analysed:

Table 1: Data to be reported: Analysis datasets and TFL’s to be produced

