3.10 Changes from the Protocol Planned Analysis

There are considerable changes from planned protocol analysis as the study was terminated early and an abbreviated CSR and SAP produced. This SAP covers only the outputs required from Veristat for reporting. The abbreviated CSR will include information from other sources, ie the results of the interim analysis. This will be documented in the CSR.

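### The SAP drops Part B's randomised ORR comparison of 40/15 with 100/20 without naming it in 3.10, and tabulates 100/20 beside a mixed 40/15 column with no randomised-only figure

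*SAP*

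**What the plan says.** **Protocol.** Section 5.3.1 sets two primary objectives for Part B. The first, for the randomised section, is to evaluate the efficacy of the 40/15 "dose regimen (40 mg lilotomab/ 15 MBq/kg Betalutin) compared with the" 100/20 regimen on IRC response. Section 14.1.7 gives its analysis: Fisher's exact test, "and the difference in response rates and the corresponding 95% exact CI will be presented". Both stand in the current version, which was written after randomisation had stopped (6.1). Section 14.1.5 commits the SAP to recording any departure from the protocol's analyses.

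**SAP.** Section 2.2 limits its scope to listed objectives: ORR of 40/15 is primary, ORR of 100/20 is a separate secondary objective, and no comparison appears. The Efficacy Analysis set (3.2.2) takes every treated Part B patient assigned to either regimen. Tables are laid out by study part and dose regimen (3.4). For ORR, section 3.7.1.2 plans "The number and percentage of responders for each dosing regimen together with the exact 95% CI using the Clopper-Pearson method", and CRR follows the same pattern (3.7.2.2).

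On changes, section 3.10 says: "There are considerable changes from planned protocol analysis as the study was terminated early and an abbreviated CSR and SAP produced". It adds: "The abbreviated CSR will include information from other sources, ie the results of the interim analysis". Section 1 had already used that term for the July 2022 review of 61 patients on 40/15: "Details of this interim analysis are documented separately".

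The SAP does disclose that randomisation stopped and later patients went to 40/15 (2.1), and that the study lacks power for its original objectives (2.4).

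**The concern.** There are two gaps. First, a protocol primary objective loses its analysis, and the section meant to record changes neither names it nor gives a reason. The pointer to interim results does not fill the gap, because it could mean the 47-patient randomised interim or the July 2022 review, which covered 40/15 only.

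Second, the planned table sets two regimens side by side that are no longer a randomised contrast. The 100/20 column closed at the interim; the 40/15 column continued. A reader who compares the rates is comparing patients from different calendar periods, after a selection in which response may have played a part. The SAP text offers no randomised-only figure and no caution.

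At stake is how the close-out report answers a stated objective. The dose decision and the single-arm estimate are not affected.

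**Working it through.** **1. The protocol's own figure.** Protocol 14.1.2.1: ORR 69% v 42%, two-sided 0.05, continuity-corrected chi-square, 65 per arm, at least 80% power.

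- Uncorrected n per arm at 80% power: [1.96√(2 × 0.555 × 0.445) + 0.8416√(0.69 × 0.31 + 0.42 × 0.58)]² / 0.27² = (1.3775 + 0.5693)² / 0.0729 = 52.
- Corrected: (52/4) × [1 + √(1 + 4/(52 × 0.27))]² ≈ 59.2, so 60.
- At 65 per arm, power is about 84% (corrected) or 83.7% (exact Fisher). The claim is met.

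**2. What the randomised data can support.** The interim had 47 patients. The split by arm is not given; 24/23 or 23/24 is assumed from the 1:1 ratio. Exact Fisher power for 69% v 42% is 43.4% or 42.1%. As an illustration, 17/24 v 10/23 is a difference of 27 points with an exact 95% interval of about -2 to +53.

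**3. How mixed the 40/15 column is.** Take 61 patients (the July 2022 count, not the final number). If 23 or 24 were randomised, 38/61 = 62% or 37/61 = 61% were not. If later patients' true ORR differed by 10 points, the pooled rate, and its gap to 100/20, would shift by 10 × 37/61 ≈ 6 points.

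**4. Selection at the interim.** Let X ~ Bin(n1, p1) for 40/15 and Y ~ Bin(n2, p2) for 100/20, and let S be the event that 40/15 is chosen. By full enumeration:

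- b1 = E[X/n1 | S] - p1 and b2 = E[Y/n2 | S] - p2
- bias of pooled 40/15 = b1 × n1/61, since later patients are unaffected by S
- bias of the side-by-side contrast = b1 × n1/61 - b2
- bias of the randomised-only difference = b1 - b2

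Two rules were tried: 40/15 has the higher ORR; or 40/15 is at or above 40% and 100/20 is below it, which is the non-binding guideline in protocol 14.1.2.2.

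Example, higher ORR, 24/23, both true rates 30%: b1 = +5.66, b2 = -5.61. Pooled 40/15: 5.66 × 24/61 = +2.23. Contrast: 2.23 + 5.61 = +7.84. Randomised-only: +11.28 (from unrounded terms).

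Example, guideline, 23/24, both 48%: b1 = +4.62, b2 = -14.21. Pooled 40/15: 4.62 × 23/61 = +1.74. Contrast: +15.96. Randomised-only: +18.83.

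Ranges over both splits, in percentage points:

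| Selection rule | True rates | Side-by-side contrast | Randomised-only difference |
|---|---|---|---|
| Higher ORR | equal, 30-48% | +7 to +8 | +10 to +12 |
| 40% guideline | equal, 30-48% | +8 to +16 | +15 to +19 |
| Higher ORR | 69% v 42% | about +0.7 | about +1 |
| 40% guideline | 69% v 42% | +9 to +10 | +9 to +10 |
| Unrelated to response | any | about 0 | about 0 |

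**The case against.** The SAP is openly abbreviated. It says randomisation stopped, limits itself to listed objectives, disclaims power, and plans no test or difference between regimens. The shells for tables, figures and listings (SAP 3.1) are a separate document that was not available, and they may carry a footnote. The dose is chosen, and a randomised-only difference would be imprecise and, under selection on response, at least as biased as the contrast it is meant to replace.

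Much of this stands. A reader might infer that the SAP conceals the mixed 40/15 group; section 2.1 shows that it does not. A reader might infer that pooling 40/15 is an error; protocol 14.1.2.3 requires it for the single-arm question. A reader might infer that Fisher's test must be restored; at about 42-43% power, leaving it out is defensible.

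What remains is that a general remark about scope and power does not tell the reader that a primary comparison was removed, or that the two columns cannot be read as a randomised contrast. A footnote in the shells would help with the second but would not meet the commitment in protocol 14.1.5.

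**Conclusion.** The point holds as a gap in documentation and labelling, and it is cheap to close. The omission in 3.10 and the mixed column follow directly from the text.

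The size of any distortion is conditional. It assumes 23 or 24 randomised per arm, no randomisation after the interim cut, and 61 patients in 40/15. Selection bias in the side-by-side contrast then runs from about 0 to +16 points, depending on the true rates and on how the choice was made. Protocol 4.8.10 names ORR among the grounds, together with safety and haematological events, and gives no interim rates. It would therefore be tempting, but unsupported, to say that 40/15 is known to be flattered by a definite amount.

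It would also be wrong to treat the randomised-only difference as the unbiased answer. It removes calendar-time confounding but carries equal or larger selection bias. Its value is that it answers the stated objective on a known footing, with its limits declared.

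**What to change.** 1. In SAP 3.7.1.2 (and for CRR in 3.7.2.2), show 40/15 split into randomised and post-interim patients, beside the pooled 40/15 and the 100/20 columns.
2. Among randomised patients in the Efficacy Analysis set, report the ORR difference with its exact 95% interval, labelled descriptive. Note that interim selection may inflate it and that the interval does not allow for this. No p-value is needed.
3. Add a footnote that pooled 40/15 against 100/20 is not a randomised comparison.
4. In 3.10, name the dropped comparison and the reason (for example early termination, low power, dose already chosen), and state which interim analysis the CSR will report.

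**Cost.** No new data. It needs a flag for randomised status, derived from a dataset that SAP Table 2 now supplies only as raw data, plus a few extra rows, one footnote and two or three sentences. The downside is an imprecise descriptive estimate in the report.

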3.7.2 Secondary Endpoint: Complete Response Rate (CRR) by IRC assessment

3.7.2.1 Definition

Complete Response Rate (CRR), defined as the proportion of participants who achieve a CR assessed with the use of standard criteria for lymphoma. The CRR will be calculated based on CR achieved at any timepoint.

3.7.2.2 Analysis

CRR will be analysed in the same manner as ORR.

3.7.3 Secondary Endpoints: Duration of Response and Duration of Complete Response by IRC assessment

3.7.3.1 Definition

DoR is the time from when criteria for response (CR or PR) is first met to the time of relapse or progression, so is therefore only defined for those participants who are responders. Participants who have not relapsed/progressed will be censored at the last adequate tumour assessment.

For those participants with documented disease progression, death or withdrawal after a response was detected during the study, duration of response (months) is defined as:

$$([First\ date\ of\ disease\ relapse - first\ date\ of\ response] + 1) * 12 / 365.25$$

Where the first date of disease relapse will be the first documented date of progressive disease or death after the response.

Participants without documented disease progression or death after a CR/PR response: censored at the date of the last CR/PR assessment, where the censoring time will be defined as follows:

$$\text{Duration of response (months)} = ([\text{Date of last assessment where the participant was assessed as a responder} - \text{first date of response}] + 1) * 12 / 365.25.$$

DoR based on complete remission (DoCR) will also be derived and in an analogous method to DoR but using only CR to determine responders.

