15. Revision of the statistical analysis section (i) to group all details in a single place to facilitate readability of it and (ii) clarify some requirements.
 - Statistical analysis methodology restructured and clarification added to explain that results from Part A (Phase I and Phase IIa), Part B and Part C will be summarised separately due to differences in study design, dose regimens and patient populations. However analyses in specific populations and for specific dose regimens may be performed in the overall study population.
 - Efficacy endpoint definitions moved to the statistical section only, removing the duplicate definitions from Section 5.6 and removing Section 12.4 from protocol Version 14; Section 14.1.7. There is no change in the definitions and no loss of information.

- Timing of analyses for Part B more clearly identified. Clarification added that the statistical analysis would be fully described in a Statistical Analysis Plan (SAP) prior to database lock; [Section 14.1.5](#).
 - “Not evaluable” added as an option for tumour response for completeness; [Section 14.1.7](#).
 - Requirement to present the primary endpoint at each timepoint removed as not necessary; [Section 14.1.7](#).
 - Handling tumour response data from patients who withdraw or are lost to follow-up as disease progression at the time of the last assessment removed; [Section 14.1.12](#). These data will be handled as censored data and relevant sensitivity analyses will be conducted.
 - Clarifications added to the definitions of the efficacy endpoints and of analysis of time-to event endpoints; [Section 14.1.7](#).
16. Addition of a new section on collection of IMP dosing errors previously omitted; [Section 16.3.6](#).

Further changes to improve sense, readability and prevent misunderstanding have also been made *without changes to overall protocol requirements*:

17. Clarifications to the rationale for a lower dose of Betalutin for patients with prior autologous-SCT and/or lower platelet counts, including the consolidation of text previously in the study design section; [Section 4.8.11](#). There is no change to the rationale previously described in Version 14.
18. Clear presentation of the design of each part of the study and of the assessments to be performed. Where procedures differ between different parts of the study, these have been separated; [Section 6.1](#).

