
DoR is the time from when criteria for response (CR or PR) is first met to the time of relapse or progression. Patients who have not relapsed/progressed will be censored at the last adequate tumour assessment.

Duration of Complete Response (DoCR)

DoCR is the time from when the complete response is first observed to the time of relapse. Patients who have not relapsed will be censored at the last adequate tumour assessment.

Overall survival (OS)

OS is defined as the time from administration of Betalutin to the date of death from any cause. Patients still alive or lost to follow-up are censored at the last date they were known to be alive. Patients still alive are censored at the last known date alive.

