3.7.4 Secondary Endpoint: Progression-free survival (PFS)

3.7.4.1 Definition

PFS is defined as the interval from Betalutin administration and date of:

- Relapse (new or enlarged lesions after CR).
- Progression (new or enlarged lesions after PR or SD).
- Death from any cause.

Documented disease progression is defined as a Relapse (after CR) or progression (after PR or SD) and is indicated at the earliest date when the response assessment is given as progressive disease (PD). Death from any cause includes deaths occurring before the first post-baseline tumour assessment. If death occurs after two or more missed tumour assessments the participant should be censored (see below). PFS for participants meeting the events definition will be derived as follows:

$$\text{Progression-free survival time (months)} = ([\text{earliest of (First date of documented disease progression or death)} - \text{date of Betalutin administration}] + 1) * 12 / 365.25.$$

If none of the above events are observed PFS will be censored as follows:

- Incomplete/no baseline tumour IRC assessments: censor at date of Betalutin administration (study day 1).
- No documented disease progression: censor at date of last tumour IRC assessment where progression was not shown.

- Death or progression after two or more missed tumour assessments: censor at date of last tumour assessment where progression was not shown.

PFS for censored participants will be derived as:

$$\text{Progression-free survival time (months)} = ([\text{Date of censoring} - \text{date of Betalutin administration}] + 1) * 12 / 365.25$$

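### SAP 3.7.3.1 places a responder who withdraws under both the duration-of-response event formula and the censoring rule; protocol 14.1.7 supports only censoring

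*SAP*

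**What the plan says.** SAP 3.7.3.1 defines DoR in four steps that do not fit together.

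- It first states a general censoring rule: "Participants who have not relapsed/progressed will be censored at the last adequate tumour assessment".
- It then gives the event formula, first date of relapse minus first date of response plus one day, converted to months. The formula applies to this group: "For those participants with documented disease progression, death or withdrawal after a response was detected during the study".
- It defines the end date of that formula as follows: "Where the first date of disease relapse will be the first documented date of progressive disease or death after the response". No date is given for withdrawal.
- It ends with a second censoring rule: "Participants without documented disease progression or death after a CR/PR response: censored at the date of the last CR/PR assessment".

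DoCR is derived in the same way, using complete responses only.

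Protocol 14.1.7 runs DoR to relapse or progression and adds: "Patients who have not relapsed/progressed will be censored at the last adequate tumour assessment". Its DoCR rule is parallel. Withdrawal is not an event in either. The rationale for protocol Version 15 (item 15) gives the background: "Handling tumour response data from patients who withdraw or are lost to follow-up as disease progression at the time of the last assessment removed". It continues: "These data will be handled as censored data and relevant sensitivity analyses will be conducted".

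For PFS, SAP 3.7.4.1 does not name withdrawal as an event, and its censoring list includes: "No documented disease progression: censor at date of last tumour IRC assessment where progression was not shown".

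**The concern.** A responder who withdraws without PD or death belongs to the group given the event formula and also to the group that is censored. The SAP does not say which rule takes precedence. The same patient is plainly censored for PFS.

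The rule drives everything reported under SAP 3.7.3.2: event and censored counts, the median and quartiles, and the rates at 3, 6, 9, 12 and 15 months. SAP 3.5.2 takes withdrawal reasons from a Completion / Withdrawal eCRF page, so a program has a withdrawal status that it could pick up. If it counts that status as relapse, or drops the patient because the end date is missing, response looks shorter-lived than it was. SAP 3.10 describes the changes from the protocol only in general terms and does not list withdrawal as an intended DoR event.

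**Working it through.** The documents state no DoR figure to reproduce, so the check has two parts.

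**1. The SAP rules applied to three kinds of responder.** The formula is months = (end day − first response day + 1) × 12 / 365.25. The days are assumed: first response Day 92, PD or death Day 400, last CR/PR scan Day 274, withdrawal Day 300.

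| Responder | Rule | Result |
|---|---|---|
| PD | event formula | (400 − 92 + 1) × 12 / 365.25 = 10.2 months, event |
| Death | event formula | 10.2 months, event |
| Withdrawal only | event formula as written | no end date, undefined |
| Withdrawal only | event formula with the withdrawal date put in | (300 − 92 + 1) × 12 / 365.25 = 6.9 months, event |
| Withdrawal only | last-CR/PR censoring sentence | (274 − 92 + 1) × 12 / 365.25 = 6.0 months, censored |

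One patient thus has three possible outcomes. Only the last agrees with protocol 14.1.7 in treating the patient as censored. The two censoring sentences also name different dates, the last adequate tumour assessment and the last CR/PR assessment. These differ if, for example, a later scan is read as stable disease.

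**2. Illustrative size.** The documents give no number of responders, no number of withdrawals and no expected DoR, so all inputs are assumptions. They are: exponential DoR with true median m; withdrawal unrelated to relapse, reaching a proportion w by 12 months in the absence of relapse; and a 24-month cut-off for the dropped-patient case.

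- Relapse hazard: λ = ln 2 / m. Withdrawal hazard: g = −ln(1 − w) / 12.
- Withdrawals censored: the median stays at m.
- Withdrawals counted as events: median = ln 2 / (λ + g), and 12-month rate = exp(−12(λ + g)).
- Withdrawals dropped: Kaplan-Meier median from 200,000 simulated responders per scenario.

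For m = 12, λ = 0.6931 / 12 = 0.0578. At w = 5%, g = 0.0513 / 12 = 0.0043, so the median is 0.6931 / 0.0620 = 11.2. At w = 30%, g = 0.3567 / 12 = 0.0297, so the median is 0.6931 / 0.0875 = 7.9.

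| w by 12 months (m = 12) | Median, censored | Median, as events | 12-month rate, as events (true 50%) | Median, dropped |
|---|---|---|---|---|
| 5% | 12.0 | 11.2 | 47.5% | 11.4 |
| 10% | 12.0 | 10.4 | 45% | 10.9 |
| 20% | 12.0 | 9.1 | 40% | 9.8 |
| 30% | 12.0 | 7.9 | 35% | 8.6 |

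With a true median of 6 months, both misreadings give 5.8 at w = 5% and 4.8 at w = 30%. The direction is downward in every scenario.

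**The case against.** The strongest reply is that the section corrects itself. No withdrawal date enters any DoR formula, and two sentences censor a responder with neither PD nor death. For that patient the only result that can be computed as written is censoring, which is what the protocol asks for. To count a relapse, a programmer would have to supply a date that the SAP does not define. Protocol 8.1 also lists death as a form of withdrawal, so some withdrawals do have a valid end date. DoR and DoCR are secondary and descriptive, in a terminated study that SAP 2.4 says is not powered for its original objectives. Event and censored counts are tabulated and derived variables are listed, so a misallocation could be seen.

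Much of this stands. Bias is possible, not certain, and the point is a modest one. It does not remove the contradiction: the event sentence still names withdrawal, nothing gives the censoring sentences priority, and the two censoring dates disagree.

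A reader might go further and infer that the July 2022 termination turns every ongoing responder into a relapse. If all exits were counted as events and spread evenly over 36 months after response, solving exp(−t ln 2 / 12) × (1 − t/36) = 0.5 takes a 12-month median to about 7.8 months. The documents do not support that inference. Nowhere do they say that responders still under follow-up at closure are recorded as withdrawals, and SAP 3.5.2 names data cut-off, death and withdrawal separately.

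The Version 15 rationale is an account of changes, so it is used here only as background. Protocol 14.1.7 carries the point alone.

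**Conclusion.** The concern holds as an internal contradiction in SAP 3.7.3.1 and a departure from protocol 14.1.7. A responder who withdraws without PD or death falls under two incompatible rules. One gives the protocol's result. The other gives no duration, or a relapse that was not observed, and would shorten DoR and DoCR.

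The effect cannot be sized from the documents. The illustrative range for a true 12-month median is 11.2 down to 7.9 months if withdrawals are counted as events, and about 11.4 down to 8.6 if they are dropped. It rests on exponential durations, withdrawal unrelated to relapse, and 5% to 30% withdrawn by 12 months. The text does not show that the reported DoR will be biased, only that the rule allows it. ORR, CRR and PFS do not depend on it.

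**What to change.** In SAP 3.7.3.1:

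- Remove withdrawal from the event sentence, so that it names progression and death only.
- State that a responder who withdraws, is lost to follow-up or leaves at study termination without IRC progression or death is censored at the last adequate tumour assessment, the date used in protocol 14.1.7.
- Use that single censoring date throughout the section, replacing the last-CR/PR date, and apply the same rule to DoCR.
- If withdrawal as an event is of interest, show it only as a labelled sensitivity analysis that uses the withdrawal date, with withdrawal defined as withdrawal other than by death.

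Keeping death in the condition follows the SAP's own end-date definition. Protocol 14.1.7 names only relapse and progression for DoR, so SAP 3.10 should record that difference.

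The cost is a few lines of SAP text and a check of the DoR and DoCR derivation program. No new data are needed.

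### SAP 3.7.3.1 gives two different censoring dates for DoR and DoCR, and counts death without progression as an event although its own opening paragraph and protocol 14.1.7 censor it

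*SAP*

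**What the plan says.** SAP 3.7.3.1 defines DoR as running from first CR or PR to relapse or progression, and states: "Participants who have not relapsed/progressed will be censored at the last adequate tumour assessment".

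The same section then gives two formulas.

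- **Event formula.** It applies to participants with "documented disease progression, death or withdrawal after a response was detected during the study". The end date is the "first documented date of progressive disease or death after the response".
- **Censoring formula.** Responders with neither PD nor death are "censored at the date of the last CR/PR assessment". The formula ends at the last assessment at which the participant was still rated a responder.

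DoCR is derived "in an analogous method to DoR but using only CR to determine responders", so it takes over both formulas.

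Protocol 14.1.7 ends DoR at relapse or progression and DoCR at relapse. For both endpoints it censors everyone else at the last adequate tumour assessment. It does not name death as an event for either one.

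For PFS, SAP 3.7.4.1 handles patients without documented progression differently: "censor at date of last tumour IRC assessment where progression was not shown". It defines relapse as lesions that appear or grow after CR, dated at the first PD assessment, and lists death as a separate event. SAP 3.10 says in general terms that there are considerable changes from the protocol. It does not mention DoR or DoCR.

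**The concern.** One section holds two rules for the same patient, and no order of precedence is stated. The second rule discards scans that show no progression, although the PFS analysis uses those same scans as follow-up.

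DoCR is more exposed. Under the second rule a patient who moves from CR to PR without progressing is censored at the last CR scan. Under the SAP's own definition of relapse that move is not an event, so the later scans are event-free follow-up.

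For death, the conflict changes event status as well as the date.

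The results at stake are those in SAP 3.7.3.2: counts of events and censored patients, the quartiles, and the rates at 3, 6, 9, 12 and 15 months. SAP section 1 sets a minimum of only 3 months' follow-up after the last 40/15 patient in Part B, so some responders will have few scans and the censoring rule matters more for them.

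**Working it through.** The plan gives no figure to reproduce. The check sets the rules side by side and then applies the SAP's formula to example patients.

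**1. The rules**

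| Source | Event | Censoring date |
|---|---|---|
| Protocol 14.1.7, DoR | relapse or progression | last adequate tumour assessment |
| Protocol 14.1.7, DoCR | relapse | last adequate tumour assessment |
| SAP 3.7.3.1, opening | relapse or progression | last adequate tumour assessment |
| SAP 3.7.3.1, formulas | PD or death | last CR/PR assessment (last CR for DoCR) |
| SAP 3.7.4.1, PFS | relapse, progression or death | last IRC assessment without progression |

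The two DoR censoring dates agree only if the last adequate scan is still CR/PR. For DoCR it must still be CR.

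**2. Example patients**

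Assumptions: the sequences are invented, scans fall on nominal weeks, week k is day 7k after Betalutin, and first response is at week 12 (day 84). Duration in months = (end day − start day + 1) × 12 / 365.25. DoR and DoCR start at day 84; PFS starts at day 0.

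*A. PR, PR, SD at weeks 12, 26, 39; no PD or death.*
- DoR, last adequate scan (day 273): 190 × 12 / 365.25 = 6.24 months.
- DoR, last CR/PR scan (day 182): 99 × 12 / 365.25 = 3.25 months.
- PFS, censored at day 273: 274 × 12 / 365.25 = 9.00 months.
- Of the reported times, the patient is at risk at 3 and 6 months under the first rule and at 3 months only under the second.

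*B. CR at week 12, then PR at weeks 26, 39, 52.*
- DoCR, last adequate scan (day 364): 281 × 12 / 365.25 = 9.23 months.
- DoCR, last CR scan (day 84): 1 × 12 / 365.25 = 0.03 months.
- PFS, censored at day 364: 365 × 12 / 365.25 = 11.99 months.
- At risk at 3, 6 and 9 months under the first rule; at none of the reported times under the second.

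*C. PR at weeks 12 and 26, death without PD on day 250.*
- Death as event: 167 × 12 / 365.25 = 5.49 months.
- Death censored at the last scan (day 182): 99 × 12 / 365.25 = 3.25 months.

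**3. Direction**

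Each Kaplan-Meier factor is 1 − d/n. With the events d fixed, earlier censoring can only reduce n, so each factor stays equal or falls. The last-CR/PR rule can therefore lower the curve but never raise it.

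**4. Possible size, on assumed data**

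Take 20 responders with PD at 3, 3, 6, 6, 9 and 9 months and the other 14 followed to 15 months. The 12-month rate is 14/20 = 70.0%.

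- *Censoring date.* Suppose j of the 14 leave the response category straight after first response without progressing. The last-CR/PR rule gives (14 − j)/(20 − j): 12/18 = 66.7% for j = 2, 10/16 = 62.5% for j = 4, 8/14 = 57.1% for j = 6. The last-adequate rule stays at 70.0%.
- *Death.* Suppose k of the 14 die without PD at 7.5 months, last scanned at 6 months. With death as an event the rate is (14 − k)/20: 65.0% for k = 1 and 50.0% for k = 4. With death censored it is 16/20 × (14 − k)/(16 − k): 69.3% for k = 1 and 66.7% for k = 4. At k = 4 the median is 9 months if death is an event and is not reached if it is censored.

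**5. Can CR to PR without PD occur?**

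Protocol 12.1.3 schedules PET at baseline and Months 3 and 6, and only CT or MRI from Month 9. In protocol Table 12-1, CR on PET allows a residual mass, while CR on CT requires target nodes of at most 1.5 cm in longest diameter. A metabolic CR with a stable residual mass could therefore be rated lower on a later CT. The documents do not say whether the IRC carries the PET result forward, so the frequency is unknown.

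**The case against.** The strongest reply is that the section should be read as a whole. A general sentence taken from the protocol is followed by an operational definition, only the second censoring rule has a formula, and a programmer would follow the formula. On that reading death is consistently an event, and what remains is an undocumented change from the protocol. This has force on what will probably be programmed. But the opening sentence is itself an explicit censoring rule. If the formulas do govern, the SAP departs from protocol 14.1.7 on both censoring and death, and protocol 14.1.5 requires the SAP to document such changes. SAP 3.10 does not list them.

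Other points:

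- *DoR and PFS may censor differently.* True, so the PFS comparison alone proves no error. It does show that the SAP accepts the same scan as valid follow-up elsewhere.
- *Not crediting PR time to DoCR is defensible, and some losses of CR are PD anyway.* Table 12-1 does count regrowth of resolved lesions as progression. Ending DoCR at any loss of CR would still be a different endpoint from the one defined, and would have to be stated.
- *The examples are chosen.* They are. With the ±7-day visit window, patient A could have (266 − 91 + 1) × 12 / 365.25 = 5.78 months under the first rule and would not be at risk at 6 months. The two rules would still give different dates.
- *Withdrawal might change results.* It sits in the event sentence, but the end date is defined only by PD or death. A withdrawn patient with neither falls under the censoring formula, so as written it has no numerical effect.
- *The stakes are modest.* The study was terminated and these are descriptive secondary endpoints. This limits the consequence but does not remove the contradiction.

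**Conclusion.** The concern holds. SAP 3.7.3.1 gives two incompatible censoring dates for DoR and DoCR. Its event definition includes death, contrary to its opening paragraph and protocol 14.1.7, and SAP 3.10 does not record the change. For one patient the difference can be about 3 months of DoR (A: 6.24 against 3.25), about 9 months of DoCR (B: 9.23 against 0.03), or a change of event status (C). These figures are exact for the assumed sequences and nominal scan days. The cohort effect cannot be given, because the documents do not report how many responders have such sequences; the Kaplan-Meier ranges only illustrate possible size. ORR and CRR do not change. The point should be corrected before the DoR and DoCR outputs are produced, but it does not bear on the primary endpoint.

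**What to change.** In SAP 3.7.3.1:

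- Delete the last-CR/PR censoring rule and its formula. Censor both DoR and DoCR at the last adequate IRC tumour assessment without progression, in line with protocol 14.1.7 and with the PFS rule for patients without documented progression. Define what makes an assessment adequate, and say whether the PFS rule on two or more missed assessments also applies.
- State one event list for DoR and one for DoCR. If death is kept as an event, which is a reasonable choice, amend the opening paragraph to match and record it in SAP 3.10 as a change from protocol 14.1.7.
- As clean-up, remove withdrawal from the event sentence, since no event date is defined for it.

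The cost is SAP wording and a small programming change. No new data are needed.
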